**OT challenge** Each subject will participate in 2 OT challenges: one at the assigned dose and the other on placebo. The challenges will be separated by one week and will occur in randomized order. A single formulation of OT will be used and dose will be adjusted by the number of nasal sprays of OT or placebo. On the day of the challenge the study staff will observe the subject as he or she applies the assigned number of sprays of OT or placebo. We do not believe that subjects will be able to discriminate OT from placebo. In a prior study [11] subjects were unable to distinguish OT from placebo. The pupillometry, EEG, and social preference measures will be administered 30 minutes following OT or placebo administration in a standardized order (see Table 2).

[figure not shown]

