cross and stimulus. Once the choice screen appears they are instructed to identify which stimulus type was shown and they can blink freely. They can then initiate the next trial when they feel they will not need to blink. This task will take approximately 20 minutes to complete.

Pupillary responses from the right eye will be continuously recorded using a ViewPoint EyeTracker USB-220 (Arrington Research, AZ), using an infrared light source and infrared camera. The recording system will be connected to the presentation computer to synchronize trigger signals that indicate the beginning of a trial. Pupillometry data will be continuously recorded at 220 Hz and stored for offline data analysis. Pupillometry data will be analyzed with custom-written scripts in Matlab. Cleaning of data (e.g., removal of blinks) and data reduction will be accomplished following standard procedures [40, 42-44]. Briefly, data will be smoothed using a 20-point moving average filter. Eyeblinks, defined as changes in pupil size that are too large and rapid to represent actual pupil dilation or constriction, will be replaced by linear interpolation. Pupil diameter, measured as the average dilation over the 0.2 s preceding the onset of the stimulus, will be subtracted from pupil diameter after stimulus onset to produce a pupil dilation difference score: positive scores indicate dilation while negative scores indicate constriction. Stimulus-locked pupillary response will be averaged for each stimulus type. Data will be analyzed as the mean change in pupil size occurring between 0.8-2.5 s after stimulus presentation.

**Pilot Data:** Pilot data are available for 8 stable schizophrenia patients on antipsychotic medication who received double-blind 40 IU of intranasal OT or placebo administered a week apart. We assessed the effects of OT on pupillary responses using the paradigm described above. First, we found that greater pupil dilation was seen to faces, compared to a scrambled face (data not shown), consistent with prior studies. Second, as can be seen in Figure 2, OT reduced pupillary dilation to fearful faces in comparison to placebo ( $d=.81$ ), consistent with OT down-regulating amygdala activation to fearful faces [18, 45] and consistent with the one previously published paper showing less dilation on OT to fearful faces [31]. While the sample size is small, these pilot data demonstrate the expected pupillary response to faces and the feasibility of OT to influence pupil size.

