**C.1.g. Social Salience measures:** For the purposes of the R21 and the R33 we will use behavioral measures of social preference to assess social salience. The two tasks, a gaze-cuing task and a one-armed bandit task, assess social orienting and social reward, respectively, and both are considered indices of social salience. As noted below, recent work in our laboratory indicates that individuals with schizophrenia are less likely than controls to show a preference for social cues.

**Gaze-cuing task:** To assess social orienting, we will use a gaze-cuing task in which subjects will be asked to indicate the location of a target (the letter X in one of two peripheral boxes) following an uninformative central cue (either social or nonsocial) [46, 47]. The social cue will be a drawing of eyes gazing left or right; the nonsocial cue will be an arrow pointing left or right. On each trial a fixation cross will be presented for 700 ms along with two peripheral boxes (left and right), followed by the cue at the center of the screen for 150 ms. After cue offset, the target will appear and remain on the screen until a response is made. Subjects will be asked to detect the location of the target as quickly and accurately as possible; both accuracy and reaction time will be

recorded. We will use 4 stimulus onset asynchronies (SOAs) between the cue and the target (i.e., SOA of 150, 250, 350, and 700 ms) to examine the time course of social orienting across SZ patients and controls as a function of the SOA. There will be 100 trials for each SOA per type of cue (social or nonsocial); there will also be 40 catch trials with a nondirectional cue to detect and exclude invalid performance. Both social and nonsocial cues are uninformative, meaning that the direction of the cue will be consistent with the target location on half of the trials (congruent condition) and inconsistent on the other half (incongruent condition). The two types of cues will be randomly presented throughout the task. The difference between congruent and incongruent conditions is the cuing effect. The dependent measure typically used is the ratio of social and nonsocial cuing effects: a ratio greater than 1.0 shows preferential orienting towards social cues. This task will take 30 minutes to complete.

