**Pilot data:** We adapted an existing task [46, 47] and collected pilot data with 3 controls and 3 schizophrenia patients who were stable on antipsychotic medication. As expected, controls showed a ratio greater than 1.0, indicating a preferential orienting for social cues. In contrast, patients showed a preference towards nonsocial stimuli (ratio <1.0) (Figure 3).

[figure not shown]
**One-armed bandit task:** To measure reactivity to social vs. nonsocial rewards, we will employ a one-armed bandit task [48, 49]. This task has two blocks with identical trial structures except for the type of reward (i.e., social or nonsocial). The order of the blocks will be counterbalanced across subjects. For the social reward block, we will use color photographs of unfamiliar faces from the NimStim collection [50], showing happy (positive outcome), angry (negative outcome) or neutral (neutral outcome) emotional expressions. For nonsocial reward, we will use: an image of a dollar bill (positive outcome), an image of a dollar bill crossed out (negative outcome), or an image of an empty rectangle (neutral outcome).

For each trial, after a fixation point (500 ms), two slot machines will appear: a “neutral” machine paired either with a “good” slot machine or a “bad” slot machine. A good slot machine has an 80% probability of a positive outcome and a 20% probability of neutral outcome; a bad slot machine has an 80% probability of negative outcome and a 20% probability of neutral outcome; and a neutral machine is always associated with neutral outcome. Subjects will have up to 2.5 seconds to choose the slot machine that will give them the optimal outcome. Then, the reward outcome will be presented for 1.5 s. The main dependent measure will be the total number of trials the subject chooses the machine with the optimal outcome (i.e., a good over a neutral machine; a neutral over a bad machine). Subjects will not be told the reward probabilities of each slot machine and need to learn them over the course of the task. All subjects will receive the same compensation regardless of their performance. This task takes 30 minutes to complete.

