**C.1.h. Data Analysis:** The primary goal of the R21 phase is to determine the dose response curve to RT for mu suppression and pupillary response. Prior to modeling the form of the curves we will obtain descriptive statistics and graphical summaries for the measures of target engagement on placebo, at each of the active doses. We will also plot the within subject change scores and the overall dose-response curve. To formally determine whether there is target engagement we will fit a logistic dose response curve to the data for each of the outcome measures. We assume that the OT dose response curve can be adequately modeled using a 4-parameter model with a lower asymptote, slope, E50 (point of half of maximum response), and upper asymptote as the parameters. However, we will also fit a 5 parameter model that allows for an asymmetry in the acceleration and deceleration of the change slope to determine whether the additional parameter is necessary to represent the empirical dose response curve. Independent of which of the models for the dose

response curve we finally choose we will determine whether there is target engagement by testing whether the upper asymptote is significantly different from zero using a z-test based on the parameter estimate and its standard error. Specifically this test allows us to determine whether there is a measurable change in the outcome variable of interest at the optimum dose of OT (where the upper asymptote is reached) while borrowing strength across all the measurement points. For the secondary aim, examining the relationship between target engagement and social salience we will use multiple linear regression models with the social salience measures as the outcomes and change in pupillary response and mu suppression in response (OT vs placebo) as the predictors, adjusted for OT dose.

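### Treatment order is randomised but enters no planned model; an order term would protect the exploratory Aim 2 regressions from a shared visit effect and tidy the variance of the primary test

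*Combined protocol and SAP*

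**What the plan says.** Section C.1.d (OT challenge) gives each subject two sessions: "The challenges will be separated by one week and will occur in randomized order". Tables 1 and 2 place the EEG, pupil, gaze-cuing and bandit tasks in the challenge session, which takes place at both visits.

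Section C.1.h (Data Analysis) then lists the model terms. The primary model is a "4-parameter model with a lower asymptote, slope, E50 (point of half of maximum response), and upper asymptote as the parameters", with a 5-parameter alternative and a z-test on the upper asymptote. For Aim 2, "we will use multiple linear regression models with the social salience measures as the outcomes"; the predictors are the changes in pupil response and mu suppression ("OT vs placebo) as the predictors, adjusted for OT dose"). No order, period, sequence or visit term appears in either analysis or in the power simulation. The only counterbalancing described is of the two bandit blocks (section C.1.g).

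C.1.h does not say whether the Aim 2 outcome is an OT-minus-placebo change, the value at the OT visit, or an average of the two visits. The Specific Aims state that Aim 2 is exploratory and does not feed the Go/No Go decision.

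**The concern.** If performance at visit 2 differs from visit 1, the OT-minus-placebo change moves up in subjects given placebo first and down in those given OT first. Two consequences follow, of unequal weight.

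- **Aim 2.** Where the visit effect touches both an engagement measure and a salience measure, order drives both sides of the regression. The fitted slope is then partly an order effect and could be read as evidence that target engagement relates to social salience. Balancing order does not prevent this.
- **Primary test.** The same movement is noise in the change scores. It widens the standard error of the upper asymptote, on which Go/No Go rests.

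The bandit task is the outcome most open to practice. "Subjects will not be told the reward probabilities of each slot machine and need to learn them over the course of the task", and "The main dependent measure will be the total number of trials the subject chooses the machine with the optimal outcome". A gain on the second exposure would enter that count directly. A social-minus-nonsocial contrast would cancel practice common to both blocks, but the section names the total.

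**Working it through.** **Inputs from the documents:** n = 48, 8 doses x 6 subjects; model terms as in C.1.h; residual variance at the two lowest and two highest doses half that at the four middle doses (Power paragraph). **Assumed:** the visit shift δ, in SDs of the change score; two-sided 5% tests; within-subject visit correlation 0.5 for the salience outcome.

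**The plan's own power figures.** The stated powers (45%, 84%, 89% and 92% at d = .24, .81, 1.03 and 1.22) could not be reproduced. Under a two-sided z-test, SE = d / (1.96 + z of power) gives 0.131, 0.274, 0.323 and 0.363, so no single standard error fits. The protocol gives no E50, slope, lower asymptote or alpha, so this reflects missing inputs and is not a demonstrated error. The point made here does not rest on these figures.

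**Aim 2, expected false slope.** Take no true association and unit residual variance. Code order -1/2 for OT-first and +1/2 for placebo-first, so each change score moves by ±δ.

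- Change outcome, one predictor shifted: slope = δx·δy / (1 + δx²). At 0.3/0.3 this is 0.09/1.09 = 0.083; at 0.5/0.5 it is 0.25/1.25 = 0.20.
- Change outcome, both predictors shifted equally: δx·δy / (1 + 2δx²). At 0.5/0.5 this is 0.25/1.5 = 0.167.
- OT-visit level: the outcome moves by only ±δy/2, so the covariance halves. At 0.5/0.5 the slope is 0.125/1.25 = 0.10.
- Average of both visits: each subject has one visit 1 and one visit 2, the shift cancels, and the slope is 0.

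**Aim 2, approximate rate (change outcome, one predictor shifted, equal shifts).** The induced correlation is r = δ²/(1 + δ²), and the noncentrality is about r√44/√(1 - r²). At 0.3 SD, r = 0.083, the noncentrality is 0.55 and rejection is about 8%. At 0.5 SD, r = 0.20, the noncentrality is 1.35 and rejection is about 25%.

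**Aim 2, simulated false-positive rate per shifted predictor** (no true association):

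| Shift, predictor / outcome (SD) | Change outcome | OT-visit level | Mean of both visits | With order term |
|---|---|---|---|---|
| 0.3 / 0.3 | 8% | 6% | 5% | 5% |
| 0.5 / 0.5 | 20-27% | 9-11% | 5% | 5% |
| 0.3 / 1.0 | 25-28% | 12-13% | 5% | 5% |
| 0.1 / 1.0 | 7% | 6% | 5% | 5% |
| one side only | 5% | 5% | 5% | 5% |

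In the second and third rows the upper figures arise with one predictor shifted and the lower with both. For the OT-visit level at 0.5/0.5 with one predictor shifted, varying the within-subject correlation from 0.3 to 0.8 gives 7-13%.

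**Primary test, variance.** An unmodelled shift of ±δ adds δ² to the change-score variance.

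- Middle doses: 1 + δ² = 1.09 / 1.25 / 2.0 at δ = 0.3 / 0.5 / 1.0.
- Outer doses (variance 0.5): 1 + δ²/0.5 = 1.18 / 1.5 / 3.0.

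**Primary test, validity.** In simulations with E50 and slope held at assumed values and order simply randomised, the mean asymptote estimate stayed at its true value (0.238 to 0.244 for d = .24, over shifts of 0 to 1.0 SD). Null rejection without the term was 4.7-5.5%. With order balanced 3:3 within dose it fell below 5% (2.2% at 0.5 SD), which is conservative, not inflated.

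**Why no power loss is quoted.** When all four parameters were fitted freely within bounds, 36-51% of fits ended on a bound and power did not rise from d = .81 to d = 1.03. Wald standard errors are unreliable there, so differences between such fits are too.

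**The case against.** The strongest reply is that nothing here is broken. Order is randomised, so the primary test is valid as planned, and no section reports a period effect. Go/No Go needs only one of two measures to succeed, which further dilutes any loss on a single test. That stands. A reader might infer that the Go/No Go test is biased or has an inflated error rate; the randomised order rules that out.

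For Aim 2, inflation needs a shift in both a predictor and the outcome, and the measures are partly protected. Mu suppression is a ratio of biological-motion to moving-circle power. The pre-stimulus pupil baseline "will be subtracted from pupil diameter after stimulus onset to produce a pupil dilation difference score". Both remove general session shifts, so only a change in the task contrast itself counts. For gaze-cuing, "The dependent measure typically used is the ratio of social and nonsocial cuing effects", which cancels practice that scales both cuing effects alike. Large bandit practice alone causes no inflation, and with a residual predictor shift of 0.1 SD the rate is only about 6-7%. This also stands and limits the size of the concern. It does not remove it, because habituation of the pupil or mu response between visits is not excluded.

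Finally, the larger figures depend on reading the outcome as a change score. C.1.h attaches the word change to the predictors only. The OT-visit reading gives smaller rates and averaging gives none. That is a fair criticism, and a reason to define the outcome.

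**Conclusion.** The omission is real and the remedy cheap, so this is a worthwhile improvement rather than the repair of an invalid analysis. The main benefit is to Aim 2: under assumed shifts of 0.3 to 0.5 SD on both sides, the false-positive rate is about 8% to 20-27% (change outcome) or about 6% to 9-11% (OT-visit level), and the order term returns it to 5% in every case examined. For the primary test the term only recovers precision, and any power loss is small unless the period shift is large.

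Two stronger readings should be avoided. The Aim 2 rates are not predictions for this trial, because the documents give no period effect and the shifts are assumptions. Nor can a specific number of power points lost on the Go/No Go test be supported, given the missing curve inputs and the unstable free fit. The pilots also used two sessions a week apart, so their SDs may already contain period variance; the stated powers that rest on them may already include any loss.

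**What to change.** Pre-specify treatment order (OT-first = -1/2, placebo-first = +1/2) as a covariate in each Aim 2 regression and in the 4- and 5-parameter change-score models used for the upper-asymptote test. State in C.1.h which form of each salience outcome Aim 2 uses (change, OT-visit value or average) and, for the bandit task, whether it is the total count or a social-minus-nonsocial contrast.

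The cost is one degree of freedom per model: residual df go from 44 to 43 in the 4-parameter curve and in the Aim 2 regression (t critical value 2.0154 to 2.0167). The power loss is negligible if there is no period effect. No extra subjects, visits or data are needed. Fixing the term before the data are analysed avoids a discretionary choice later.

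The term handles an additive visit effect common to all doses. It does not address carryover or a dose-by-period interaction.

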**Table 2: Timeline of Oxytocin Challenge Procedures**

Time (minutes)	Procedure
0	Drug administration, setting up of EEG electrodes
30	Biological Motion Mu Suppression
45	Pupillometry Task
65	Gaze-cuing task
95	One-armed bandit task

**C.1.e. EEG Mu Suppression Task** To assess mu suppression, we will use a biological motion task in which subjects will be asked to identify either the gender, the emotion (happy or sad), or intention (moving towards or away) of a point-light walker. This paradigm has been validated in a previous study to show greater mu suppression when viewing biological versus non-biological motion, and greater mu suppression when subjects were administered OT [37]. Stimuli consist of 5 s video clips. Each video clip contains all three dimensions, e.g. a clip can show a sad woman walking toward the observer, a happy man walking away, etc. Additionally, a non-biological motion clip will be used as a control stimulus, and consists of dots moving in a circle either to the left or right of the screen. Clips will be presented on a monitor approximately 70 cm from the participant. E-Prime will be used for stimulus presentation and for syncing of triggers with the EEG equipment.

Stimuli will be presented in four separate randomized blocks, with each

**Figure 1: Biological Motion Mu Suppression**

[figure not shown]
block consisting of a separate task, requiring the subject to identify only one dimension (e.g., identify only gender, only emotion, only intention, direction of circle). A total of 23-26 clips per block will be administered. Twenty of the clips will be of one level of the dimension (e.g., male walkers) while 3-6 clips will be of the other level (e.g., female walkers). The participants are instructed to silently count the number of occurrences of the rare event and report this at the end of the block to ensure that they are attending to the task. This task will take approximately 15 minutes to complete.

EEG data will be initially filtered with a 0.5 Hz high-pass filter and re-referenced to the mastoids. Eyeblinks will be corrected using standard algorithms [38]. Artifacts exceeding  $\pm 100 \mu\text{V}$  in amplitude at any electrode site will be rejected. As in prior studies the first 10 s of each block will not be analyzed to remove potential confounds of attentional shifts due to initiation of the stimuli [37, 39]. The first 2 s of each remaining 5 s clip will be analyzed [37]. A fast Fourier transform (FFT) using a Hanning window will be performed in 0.5 Hz intervals. Integrated power between 8-10, 10-12, and 15-25 Hz range will be assessed. Mu suppression will be calculated as the  $\log_{10}$  ratio of the power during the biological motion clips relative to the moving circle clips. This ratio is intended to account for individual differences in EEG power as well as normalize ratio data that are not typically normally distributed. A negative number indicates mu suppression. Six electrode sites will be examined: C3, Cz, C4 (where mu suppression is expected), and O1, Oz, and O2 (where typical alpha modulation is seen).

EEG activity will be collected continuously throughout the session and amplified using a 64-channel BioSemi ActiveTwo amplifier (BioSemi, Germany). Data will be sampled at 1,024 Hz with filter settings of DC to 100 Hz. Sixty-four cap-mounted Ag-AgCl electrodes will be positioned using a modified international 10-20 system placement scheme. Additionally, four electrodes will be used to measure horizontal electrooculogram (EOG; placed on the outer canthus of the left and right eye) and vertical EOG (placed above and below the left eye). All electrodes will be referenced using common mode rejection during EEG recording and rereferenced offline to linked-mastoids. Data will be processed using Brain Vision Analyzer 2.

**Pilot Data:** We collected pilot data in 11 stable schizophrenia patients who were receiving an antipsychotic medication. After we obtained informed consent, subjects were administered 40 IU of OT or placebo in randomized order on 2 occasions separated by one week. The mu suppression paradigm was administered approximately 30 minutes following the nasal spray. As can be seen in Figure 1, mu suppression was greater than placebo in all three tasks, with an average effect size of  $d = 0.24$ .

**C.1.f Pupillometry Task** To assess pupil dilation to social stimuli, we will administer a facial affect identification task. This paradigm has been modified and adapted from previously published studies in healthy controls [40]. Stimuli will consist of male and female faces depicting happy, afraid, or neutral expressions, drawn from the Japanese and Caucasian Facial Expressions of Emotion and Neutral Faces dataset [41]. Additionally, the same stimuli have been scrambled to use as control stimuli. A dark grey background will be used throughout the experiment. Stimuli will be presented on a monitor approximately 70 cm from the participant. E-Prime will be used for stimulus presentation and for syncing with the pupillometry system.

Sixteen of each stimulus type will be shown in a randomized order. Each trial begins with a 3 s fixation cross followed by the presentation of the stimulus for 5 s. After stimulus offset, a screen will be shown with written options for type of stimulus. Participants will be instructed to not blink during the presentation of the fixation

[figure not shown]
cross and stimulus. Once the choice screen appears they are instructed to identify which stimulus type was shown and they can blink freely. They can then initiate the next trial when they feel they will not need to blink. This task will take approximately 20 minutes to complete.

Pupillary responses from the right eye will be continuously recorded using a ViewPoint EyeTracker USB-220 (Arrington Research, AZ), using an infrared light source and infrared camera. The recording system will be connected to the presentation computer to synchronize trigger signals that indicate the beginning of a trial. Pupillometry data will be continuously recorded at 220 Hz and stored for offline data analysis. Pupillometry data will be analyzed with custom-written scripts in Matlab. Cleaning of data (e.g., removal of blinks) and data reduction will be accomplished following standard procedures [40, 42-44]. Briefly, data will be smoothed using a 20-point moving average filter. Eyeblinks, defined as changes in pupil size that are too large and rapid to represent actual pupil dilation or constriction, will be replaced by linear interpolation. Pupil diameter, measured as the average dilation over the 0.2 s preceding the onset of the stimulus, will be subtracted from pupil diameter after stimulus onset to produce a pupil dilation difference score: positive scores indicate dilation while negative scores indicate constriction. Stimulus-locked pupillary response will be averaged for each stimulus type. Data will be analyzed as the mean change in pupil size occurring between 0.8-2.5 s after stimulus presentation.

**Pilot Data:** Pilot data are available for 8 stable schizophrenia patients on antipsychotic medication who received double-blind 40 IU of intranasal OT or placebo administered a week apart. We assessed the effects of OT on pupillary responses using the paradigm described above. First, we found that greater pupil dilation was seen to faces, compared to a scrambled face (data not shown), consistent with prior studies. Second, as can be seen in Figure 2, OT reduced pupillary dilation to fearful faces in comparison to placebo ( $d=.81$ ), consistent with OT down-regulating amygdala activation to fearful faces [18, 45] and consistent with the one previously published paper showing less dilation on OT to fearful faces [31]. While the sample size is small, these pilot data demonstrate the expected pupillary response to faces and the feasibility of OT to influence pupil size.

**C.1.g. Social Salience measures:** For the purposes of the R21 and the R33 we will use behavioral measures of social preference to assess social salience. The two tasks, a gaze-cuing task and a one-armed bandit task, assess social orienting and social reward, respectively, and both are considered indices of social salience. As noted below, recent work in our laboratory indicates that individuals with schizophrenia are less likely than controls to show a preference for social cues.

**Gaze-cuing task:** To assess social orienting, we will use a gaze-cuing task in which subjects will be asked to indicate the location of a target (the letter X in one of two peripheral boxes) following an uninformative central cue (either social or nonsocial) [46, 47]. The social cue will be a drawing of eyes gazing left or right; the nonsocial cue will be an arrow pointing left or right. On each trial a fixation cross will be presented for 700 ms along with two peripheral boxes (left and right), followed by the cue at the center of the screen for 150 ms. After cue offset, the target will appear and remain on the screen until a response is made. Subjects will be asked to detect the location of the target as quickly and accurately as possible; both accuracy and reaction time will be

recorded. We will use 4 stimulus onset asynchronies (SOAs) between the cue and the target (i.e., SOA of 150, 250, 350, and 700 ms) to examine the time course of social orienting across SZ patients and controls as a function of the SOA. There will be 100 trials for each SOA per type of cue (social or nonsocial); there will also be 40 catch trials with a nondirectional cue to detect and exclude invalid performance. Both social and nonsocial cues are uninformative, meaning that the direction of the cue will be consistent with the target location on half of the trials (congruent condition) and inconsistent on the other half (incongruent condition). The two types of cues will be randomly presented throughout the task. The difference between congruent and incongruent conditions is the cuing effect. The dependent measure typically used is the ratio of social and nonsocial cuing effects: a ratio greater than 1.0 shows preferential orienting towards social cues. This task will take 30 minutes to complete.

**Pilot data:** We adapted an existing task [46, 47] and collected pilot data with 3 controls and 3 schizophrenia patients who were stable on antipsychotic medication. As expected, controls showed a ratio greater than 1.0, indicating a preferential orienting for social cues. In contrast, patients showed a preference towards nonsocial stimuli (ratio <1.0) (Figure 3).

[figure not shown]
**One-armed bandit task:** To measure reactivity to social vs. nonsocial rewards, we will employ a one-armed bandit task [48, 49]. This task has two blocks with identical trial structures except for the type of reward (i.e., social or nonsocial). The order of the blocks will be counterbalanced across subjects. For the social reward block, we will use color photographs of unfamiliar faces from the NimStim collection [50], showing happy (positive outcome), angry (negative outcome) or neutral (neutral outcome) emotional expressions. For nonsocial reward, we will use: an image of a dollar bill (positive outcome), an image of a dollar bill crossed out (negative outcome), or an image of an empty rectangle (neutral outcome).

For each trial, after a fixation point (500 ms), two slot machines will appear: a “neutral” machine paired either with a “good” slot machine or a “bad” slot machine. A good slot machine has an 80% probability of a positive outcome and a 20% probability of neutral outcome; a bad slot machine has an 80% probability of negative outcome and a 20% probability of neutral outcome; and a neutral machine is always associated with neutral outcome. Subjects will have up to 2.5 seconds to choose the slot machine that will give them the optimal outcome. Then, the reward outcome will be presented for 1.5 s. The main dependent measure will be the total number of trials the subject chooses the machine with the optimal outcome (i.e., a good over a neutral machine; a neutral over a bad machine). Subjects will not be told the reward probabilities of each slot machine and need to learn them over the course of the task. All subjects will receive the same compensation regardless of their performance. This task takes 30 minutes to complete.

**Pilot Data:** We adapted an existing one-armed bandit task [48, 51] and piloted it with 4 controls and 7 stable schizophrenia patients on antipsychotic medication (Figure 4). For the social reward condition, the patients chose the optimal outcome much less frequently than the controls did; but the two groups did not differ on the nonsocial reward condition.

